2. SCHEDULE OF VISITS AND ASSESSMENTS

Study Procedure	Screen	Baseline Day 1	Week 1 Day 8	Week 2 Day 15	Week 4 Day 29/ET
Visit	1	2	3	4	5
Visit Window	-30 days	N/A	± 3 days	± 3 days	± 3 days
Parents/Caregivers informed consent	X				
Demographics	X				
Medical and surgical history	X				
Physical examination ^a	X	X			X
I/E criteria	X	X			
Hematology and Serum Chemistries ^b	X				
Vital signs, weight, height ^c	X	X	X	X	X
vIGA-AD ^d , EASI ^d , BSA ^d , SCORAD ^d	X	X	X	X	X
WI-NRS pruritus ^e	X	X	X	X	X
POEM ^f	X	X	X	X	X
Local Tolerability Assessments ^g		X	X	X	X
CDLQI ^h , IDQoL ^h , DFI ^h	X	X	X	X	X
Medical Photography ⁱ		X	X		X
Drug application and Parents/Caregivers training in clinic ^j		X	X	X	
Dispense/Redisperse investigational product kit ^k		X	X	X	X ^l
Weigh investigational product tubes ^l		X	X	X	X
Dispense/review diary	X	X	X	X	X
Compliance determination ^m			X	X	X
Adverse event assessment ⁿ	X	X	X	X	X
Concomitant medications	X	X	X	X	X
Study Exit ^o					X

- a. Limited physical examination: skin (including assessment of Fitzpatrick skin type at Screening only), lungs, and heart only.
- b. To be collected at Screening. In addition, laboratory safety tests may be performed at various unscheduled time points, if deemed necessary by the Investigator.
- c. Height will be collected at Screening and Week 4/Day 29. Weight should be obtained using a calibrated weight scale and the same scale should be used for a subject throughout the duration of the study. The subject should remove shoes and heavy clothing (sweaters or jackets), and empty pockets. The subject should stand with both feet in the center of the scale with their arms at their side and hold still. Record the weight to the nearest decimal fraction (for example, 25.1 kilograms). Measure the weight in triplicate and report the average weight in EDC. A 5% weight loss (whether or not intentional or other explained) should be reported to the medical monitor in a timely manner and before the next clinic visit.

Footnotes from above table:

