6.6.2. Exclusion Criteria

1. Subjects with any serious medical condition or clinically significant laboratory, vital signs, or physical examination abnormality that would prevent study participation or place the subject at significant risk, as judged by the Investigator.
2. Subjects who cannot discontinue medications and treatments prior to the Baseline visit and during the study according to Excluded Medications and Treatments ([Table 2](#)).
3. Has unstable AD or any consistent requirement for high potency topical steroids to manage AD signs or symptoms.
4. Subjects who have significant active systemic or localized infection (e.g., molluscum contagiosum), including known actively infected AD, or have had any infection that required oral or intravenous administration of antibiotics, antifungal or antiviral agents within 14 days prior to Baseline/Day 1 and during the study.
5. Subjects who are unwilling to refrain from prolonged sun exposure for 4 weeks prior to Baseline/Day 1 and during the study.
6. Subjects with skin conditions other than AD that would interfere with evaluations of the effect of the study medication on AD, as determined by the Investigator. Subjects with any condition on the treatment area which, in the opinion of the Investigator, could confound efficacy measurements, e.g., molluscum contagiosum.
7. Subjects with known genetic dermatological conditions that overlap with AD, such as Netherton syndrome.
8. Known allergies to excipients in ARQ-151 cream [REDACTED]
[REDACTED]
[REDACTED]

9. Subjects who cannot discontinue the use of strong cytochrome P-450 CYP3A4 inhibitors e.g., indinavir, nelfinavir, ritonavir, clarithromycin, itraconazole, ketoconazole, nefazodone, saquinavir, suboxone and telithromycin for 2 weeks prior to the baseline visit and during the study period.
10. Subjects who cannot discontinue the use of strong cytochrome P-450 CYP3A4 inducers e.g., efavirenz, nevirapine, glucocorticoids, barbiturates (including phenobarbital), phenytoin, and rifampin and carbamazepine for 2 weeks prior to the baseline visit and during the study period.
11. Subjects who have received oral roflumilast (Daxas®, Daliresp®) within the past 4 weeks prior to Baseline/Day 1.
12. Known or suspected:
 - Severe renal insufficiency
 - Severe renal insufficiency is defined as calculated creatinine clearance <30 mL/min
 - Moderate to severe hepatic disorders (Child-Pugh B or C)
13. Previous treatment with ARQ-151.

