7.1.5. Laboratory Tests

All tests listed below will be performed according to the Schedule of Visits and Assessments ([Section 2](#)) unless otherwise noted. No food restrictions are required for the collection of specimens. In addition, laboratory safety tests may be performed at various unscheduled time points, if deemed necessary by the Investigator.

Hematology	Serum Chemistry
Hemoglobin	Blood Urea Nitrogen
Hematocrit	Bilirubin (total and direct)
Total and differential leukocyte count	Alkaline phosphatase
Red blood cell count with indices and morphology	Aspartate aminotransferase
Platelet count	Alanine aminotransferase
	Albumin
	Sodium
	Potassium
	Chloride
	Glucose
	Creatinine (including GFR (Schwartz) or Schwartz creatinine clearance)

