7.8. Treatment Stopping Rules

If a subject has non-cutaneous adverse events of concern, clinically significant laboratory values or any condition that the investigator determines could possibly be related to the study drug, the Investigator should immediately contact the Medical Monitor to discuss if the subject should be discontinued from treatment with investigational product.

Treatment for any individual subject will be discontinued if the subject experiences:

- A serious adverse event (SAE) or a clinically significant non-serious AE which in the opinion of the Principal Investigator or Medical Monitor warrants discontinuation from the study for that subject's well-being.
- A treatment-emergent severe (Grade 3) laboratory abnormality (confirmed by repeat sample; see [Appendix 8](#) and the Laboratory Toxicity Grading section in the appendix for more information).

Parents/caregivers will be advised to promptly report any changes in behavior that could signal psychological distress or emotional distress.

Treatment should be interrupted:

- If a subject develops an application site reaction with the clinical appearance of an 'irritation reaction', and with a severity of a Dermal Response Score of 5 (erythema, edema and papules) or greater on the scale of Berger and Bowman, treatment should be interrupted for up to one week and may then be resumed if the reaction has, in the opinion of the Investigator, adequately resolved.

Treatment should be discontinued:

- If the application site reaction reoccurs, treatment should be discontinued permanently, and the subject followed until the reaction resolves.

For cases of suspected allergic contact dermatitis, the medical monitor and sponsor should be notified and there should be discussion about performing patch testing to further evaluate. Patch testing is encouraged in such cases.

In the event of a medical emergency where unblinding is required to provide medical care to the subject, refer to the most current IWRS User Manual ([Section 6.5](#)). Contact the Medical Monitor and the Sponsor promptly.

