APPENDIX 8. NIAID DMID TOXICITY TABLE

NATIONAL INSTITUTE OF ALLERGY AND INFECTIOUS DISEASES, DIVISION OF MICROBIOLOGY AND INFECTIOUS DISEASES (DMID) Toxicity Table for Use in Trials - Modified

ABBREVIATIONS USED IN FOLLOWING TABLES:

Abbreviation/Term	Definition/Explanation	Abbreviation/Term	Definition/Explanation
ALT	alanine aminotransferase	LO	Low
aPTT	activated partial thromboplastin time	mEq	Milliequivalent
AST	aspartate aminotransferase	mmHg	millimeter of mercury
AV block	atrioventricular block	[name]
bpm	beats per minute	N	Normal
BUN	blood urea nitrogen	PT	prothrombin time
CK	creatine kinase	PTT	partial thromboplastin time
CPK	creatine phosphokinase	QTc	QT-interval corrected for heart rate
FEV ₁	forced expiratory volume in 1 second	QTcB	Bazett's corrected QT interval
g	Gram	QTcF	Fridericia's corrected QT interval
HI	High	RBC	red blood cell
HPF	high power field	Rx	Therapy
IU	international unit	S	Second
IV	Intravenous	U	Unit
K/CUMM	$\times 10^3/\text{mm}^3$	ULN	upper limit of normal
LLN	lower limit of normal		

ESTIMATING SEVERITY GRADE

For abnormalities NOT found elsewhere in the Toxicity Tables use the scale below to estimate grade of severity:

- GRADE 1** **Mild:** Transient or mild discomfort (<48 hours); no medical intervention/therapy required
- GRADE 2** **Moderate:** Mild to moderate limitation in activity - some assistance may be needed; no or minimal medical intervention/therapy required
- GRADE 3** **Severe:** Marked limitation in activity, some assistance usually required; medical intervention/therapy required hospitalizations possible.

LABORATORY RANGES

Where discrepancies in the ULN and LLN of laboratory ranges occur between those included in this document and those of the laboratory that performs the assays, the values provided by the laboratory will be used for assignment of severity grade.

CLINICAL ADVERSE EVENTS

Cardiovascular	Mild (Grade 1)	Moderate (Grade 2)	Severe (Grade 3)
Arrhythmia	-	Asymptomatic, transient signs, no Rx required	Recurrent/persistent; symptomatic Rx required
Hemorrhage, blood loss	Estimated blood loss \leq 100 mL	Estimated blood loss $>$ 100 mL, no transfusion required	Transfusion required

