Blood, Serum, or Plasma Chemistries ^a	LO/HI/N ^b	Mild (Grade 1) ^c	Moderate (Grade 2)	Severe (Grade 3)
Sodium (mEq/L or mmol/L)	LO	131-<LLN	130	<130
	HI	>ULN-148	149-150	>150
Potassium (mEq/L or mmol/L)	LO	<LLN-3.2	<3.2-3.1	<3.1
	HI	>ULN-5.6	>5.6-5.7	>5.7
Glucose (mg/dL)	LO mmol/L	<LLN-3.0	<3.0-2.2	<2.2
	HI mmol/L	>ULN-8.9	>8.9-13.9	>13.9
Blood urea nitrogen	HI mmol/L	>8.9-17.8	>17.8-35.5	>35.5

Blood, Serum, or Plasma Chemistries ^a	LO/HI/N ^b	Mild (Grade 1) ^c	Moderate (Grade 2)	Severe (Grade 3)
Creatinine	N	115-151 (μmol/L)	152-177 (μmol/L)	> 177 (μmol/L)
Calcium (CTCAE 4.0)	LO mmol/L	<LLN-2.0	<2.0-1.75	<1.75
	HI mmol/L	>ULN-2.9	>2.9-3.1	>3.1
Magnesium (CTCAE 4.0)	LO mmol/L	<LLN-0.5	<0.5-0.4	<0.4
Phosphorous (CTCAE 4.0)	LO mmol/L	<LLN-0.8	<0.8-0.6	<0.6
Creatine kinase (CPK or CK) (CTCAE 4.0)	HI	>ULN-2.5xULN	>2.5xULN-5xULN	>5xULN
Albumin	LO g/L	<30-28	<28-25	<25
Total protein	LO g/L	<LLN-52	<52-50	<50
Alkaline phosphatase (U/L) (CTCAE 4.0)	HI	>ULN-2.5xULN	>2.5xULN-5xULN	>5xULN
AST (U/L) (CTCAE 4.0)	HI	>ULN-3xULN	>3xULN-5xULN	>5xULN
ALT (U/L) (CTCAE 4.0)	HI	>ULN-3xULN	>3xULN-5xULN	>5xULN
Bilirubin, serum total (mmol/L) (CTCAE 4.0)	HI mmol/L	>ULN-1.5xULN	>1.5xULN-3xULN	>3xULN
Bilirubin, serum total (mg/dL) when ALT ≥105 (Hy's law)	HI	1.3-1.5	1.6-2.0	>2.0
Bilirubin, serum direct (mmol/L) (CTCAE 4.0)	HI mmol/L	>ULN-1.5xULN	>1.5xULN-3xULN	>3xULN
Amylase (U/L) (CTCAE 4.0)	HI	>ULN-1.5xULN	>1.5xULN-2xULN	>2xULN
Lipase (U/L) (CTCAE 4.0)	HI	>ULN-1.5xULN	>1.5xULN-2xULN	>2xULN

Blood, Serum, or Plasma Chemistries ^a	LO/HI/N ^b	Mild (Grade 1) ^c	Moderate (Grade 2)	Severe (Grade 3)
Uric acid (mg/dL/mmol/L) (CTCAE 4.0)	HI	>ULN – 10 mg/dL (0.59 mmol/L) without physiologic consequences	-	>ULN – 10 mg/dL (0.59 mmol/L) with physiologic consequences

^a Depending upon the laboratory used, references ranges, eligibility ranges and grading may be split out by sex and/or age.

^b Low, High, Not Graded (N).

^c If initial boundary of grade 1 has gap from reference range or eligibility range, calculations based on the New England Journal of Medicine (NEJM) reference ranges.

Hematology	LO/HI/N ^a	Mild (Grade 1) ^b	Moderate (Grade 2)	Severe (Grade 3)
Hemoglobin (women) (g/dL)	LO	10.8-11.3	9.2-10.7	<9.2
	LO	12.0-12.5	10.0-11.9	<10.0
White blood cell count (K/CUMM)	HI	11.00-15.00	15.00-20.00	>20.00
	LO	2.50-3.50	1.50-2.49	<1.50
Lymphocytes (K/CUMM)	LO	0.76-0.90	0.50-0.75	<0.5
Neutrophils (K/CUMM)	LO	1.50-1.95	1.00-1.49	<1.00
Eosinophils (K/CUMM)	HI	0.58-0.74	0.75-1.50	>1.50

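### The creatinine cut-offs behind the Grade 3 stop are fixed values, so under stated Schwartz assumptions a child aged 2 to 5 can fall below clearance 30 without reaching Grade 3

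*Protocol*

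**What the plan says.** Protocol Section 7.8 lists the events for which an individual child's treatment will be discontinued. One is "A treatment-emergent severe (Grade 3) laboratory abnormality (confirmed by repeat sample; see" Appendix 8).

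The Appendix 8 creatinine row starts Grade 1 at "115-151 (μmol/L"), puts Grade 2 at 152-177 and Grade 3 above 177 μmol/L. In the same table AST, ALT, alkaline phosphatase, creatine kinase and bilirubin are graded in multiples of the ULN. The creatinine row carries the code N, which footnote b explains as not graded and the appendix's abbreviation list as normal. Neither meaning fits a row with three printed grades.

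Two general rules in Appendix 8 could bear on this row:

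- Where reference limits differ between the appendix and the laboratory, "the values provided by the laboratory will be used for assignment of severity grade".
- Footnote a says that, depending on the laboratory, "grading may be split out by sex and/or age".

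Renal function appears in two other places. Section 7.1.5 lists "Creatinine (including GFR (Schwartz) or Schwartz creatinine clearance") in the chemistry panel, without giving the constant. Exclusion 12 in Section 6.6.2 reads: "Severe renal insufficiency is defined as calculated creatinine clearance <30 mL/min".

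On timing, footnote b of the Section 2 schedule says of hematology and chemistry: "To be collected at Screening. In addition, laboratory safety tests may be performed at various unscheduled time points, if deemed necessary by the Investigator".

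**The concern.** A given creatinine value means a lower clearance in a shorter child, which is why the Schwartz method includes height. The protocol has the Schwartz value reported, yet the grade that drives the automatic stop uses creatinine alone, with the same three bands for every child. If the top of Grade 2 corresponds to a clearance well under 30 at the heights of this age group, the automatic stop would not fire for a child whose renal function has dropped to a level that the protocol itself calls severe. The decision to stop would then rest on clinical judgment. This concerns the safety of individual children; the efficacy analysis is not affected.

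**Working it through.** **Inputs from the protocol.** Age 2 to 5 years (Section 6.6.1). Creatinine bands 115-151, 152-177 and above 177 μmol/L (Appendix 8). Severe renal insufficiency at clearance below 30 (exclusion 12). Schwartz as the method (Section 7.1.5). The 177 μmol/L limit is printed without a derivation, so there is no plan figure to reproduce.

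**Assumptions, none given in the documents.** Schwartz constant k from 0.413 to 0.55; height 80-125 cm for this age group; clearance indexed to 1.73 m²; 88.4 μmol/L per mg/dL of creatinine.

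**Formula.** Clearance = k × height (cm) × 88.4 / creatinine (μmol/L).

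**Step 1: clearance at the top of Grade 2 (177 μmol/L).** At 100 cm:

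- k = 0.413: 0.413 × 100 × 88.4 / 177 = 20.6
- k = 0.55: 0.55 × 100 × 88.4 / 177 = 27.5

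Both are below 30, and neither is Grade 3.

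**Step 2: creatinine at which clearance equals 30.** Creatinine = k × height × 88.4 / 30.

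| k | Height (cm) | Creatinine at clearance 30 (μmol/L) | Grade there | Clearance at 177 μmol/L |
|---|---|---|---|---|
| 0.413 | 80 | 97 | none | 16.5 |
| 0.413 | 100 | 122 | 1 | 20.6 |
| 0.413 | 125 | 152 | 1/2 boundary | 25.8 |
| 0.55 | 80 | 130 | 1 | 22.0 |
| 0.55 | 100 | 162 | 2 | 27.5 |
| 0.55 | 125 | 203 | 3 | 34.3 |

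**Step 3: height at which each cut-off matches clearance 30.** Height = 30 × cut-off / 88.4 / k.

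- k = 0.413: 115 μmol/L matches at 94.5 cm, 152 at 124.9 cm and 177 at 145.4 cm. The last lies outside the assumed range, so the mismatch covers all of 80-125 cm. Below 94.5 cm, clearance passes under 30 before creatinine reaches Grade 1.
- k = 0.45, as an intermediate value: 177 matches at 133.5 cm, again outside the range.
- k = 0.55: 115 matches at 71.0 cm (below the range), 152 at 93.8 cm and 177 at 109.2 cm. A child below 93.8 cm is in Grade 1 when clearance reaches 30, and one between 93.8 and 109.2 cm is in Grade 2. Above 109.2 cm creatinine is already over 177 by then, so there is no mismatch.

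**Step 4: do the general rules in Appendix 8 repair the row?** The laboratory override concerns upper and lower limits of normal, and this row contains neither. Footnote a permits an age split, but none is printed for creatinine. Footnote c deals with a gap between the reference range and the start of Grade 1; it does not move the Grade 3 limit. The heading of the laboratory section says that some values were adapted for the laboratory or for children, without naming creatinine.

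**The case against.** The strongest reply is that clearance 30 is not the protocol's yardstick for Grade 3. Exclusion 12 governs entry, and two thresholds with different purposes do not contradict each other. That stands. A reader might infer that the protocol contradicts itself or has a second stopping rule at clearance 30; it has neither. Clearance 30 serves here only because it is the one level that the protocol labels severe.

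The size also depends on inputs from outside the documents. With k = 0.55 there is no mismatch above about 109 cm, and nothing in the documents shows how many children would be affected. That stands too.

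Section 7.8 has other routes. For clinically significant laboratory values, "the Investigator should immediately contact the Medical Monitor to discuss if the subject should be discontinued from treatment with investigational product". Treatment is also stopped for a clinically significant non-serious adverse event that the principal investigator or Medical Monitor judges to warrant it. So it would be wrong to infer that a child with failing kidneys would simply stay on treatment. These routes rest on judgment, however, and do not correct the automatic rule.

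Two further readings are tempting but unsupported:

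- The code N might suggest that creatinine is never graded. With three grades printed, a reader would grade it, and HI is almost certainly what was meant.
- Exclusion 12 gives plain mL/min, and reading it without indexing might seem to widen the gap. That shows only that unindexed clearance is a poor yardstick for small children, not that Appendix 8 is at fault.

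**Conclusion.** The point holds in limited form. The row feeding a mandatory stop uses fixed creatinine cut-offs that take no account of age or height, and the general rules in Appendix 8 do not change that. Under the assumptions listed, a child can be below clearance 30 without reaching Grade 3, throughout 80-125 cm with k = 0.413 and only below about 109 cm with k = 0.55.

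The practical impact is very small. Chemistry is scheduled at Screening only, so a treatment-emergent Grade 3 creatinine needs an unscheduled draw and a confirming repeat within a four-week treatment period, in a child without known or suspected severe renal insufficiency at entry. Very few events are expected. The row still merits correction: an on-treatment creatinine will mostly be drawn because the investigator thought it necessary, and that is when the grade should be right. The N code is an editorial slip.

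**What to change.** State in Appendix 8 and Section 7.8 that a confirmed treatment-emergent Schwartz clearance below 30 mL/min/1.73 m² counts as Grade 3, in addition to creatinine above 177 μmol/L. Express the lower grades as multiples of the age-specific ULN, with the multiples set by the sponsor's medical team. Change N to HI in the creatinine row as an editorial correction.

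The cost is one appendix row and one sentence in Section 7.8. No new test is needed, because the Schwartz value is already in the chemistry panel and height is measured at Screening. The downside is that a few more unscheduled creatinine results would be graded or would lead to a stop.

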QD	Once Daily
SAE	Serious Adverse Event
SAP	Statistical Analysis Plan
SAS	Statistical Analysis System®
SCORAD	Scoring Atopic Dermatitis
SD	Standard Deviation

 Innovaderm Research ■■■	STATISTICAL ANALYSIS PLAN, Version 1.0
Protocol Number: ARQ-151-315	Sponsor: Arcutis Biotherapeutics, Inc.

SOC	System Organ Class
TEAE	Treatment Emergent Adverse Event
TESAE	Treatment Emergent Serious Adverse Event
TLF	Tables, Listings, and Figures
WHO-DD	World Health Organization Drug Dictionary
WI-NRS	Worst Itch - Numeric Rating Score
vIGA-AD	Validated Investigator Global Assessment scale for Atopic Dermatitis

1 INTRODUCTION

This Statistical Analysis Plan (SAP) describes the planned analysis and reporting for Arcutis Biotherapeutics, Inc. clinical protocol ARQ-151-315. The analyses described in the SAP are based upon the protocol Amendment 2 dated 10 April 2023. In case of changes (note that any such changes are described in section 3.5 below) between the protocol and the SAP, the SAP will be used to guide the statistical analysis. Any deviations from the SAP will be described and justified in the final Clinical Study Report (CSR), as appropriate.

This SAP has been developed prior to database lock, unblinding, and associated analyses. All final analyses will be performed after approval of the SAP, the clinical trial data are entered into the database, any discrepancies in the data are resolved, determination of the inclusion/exclusion of each subject from each analysis population, the database is locked, and the unblinding request form is signed.

2 STUDY OBJECTIVES AND ENDPOINTS

OBJECTIVES	ENDPOINTS
Efficacy	
To assess the efficacy of ARQ-151 cream 0.05% vs vehicle administered once daily (QD) x 4 weeks to subjects aged 2-5 years with atopic dermatitis (AD).	
Primary efficacy endpoint:
 
 Validated Investigator Global Assessment scale for Atopic Dermatitis (vIGA-AD) Success, defined as a vIGA-AD score of 'clear' (0) or 'almost clear' (1) plus at least a 2-grade improvement from Baseline at Week 4 
Secondary efficacy endpoints:
 
 In subjects with a vIGA-AD score of 'Moderate' at randomization, vIGA-AD Success at Week 4 Achievement of at least a 75% reduction in the Eczema Area and Severity Index (EASI-75) at Week 4 vIGA-AD of 'clear' or 'almost clear' at Week 4 vIGA-AD Success at Week 2 vIGA-AD of 'clear' or 'almost clear' at Week 2 vIGA-AD Success at Week 1

 Innovaderm Research ■■■	STATISTICAL ANALYSIS PLAN, Version 1.0
Protocol Number: ARQ-151-315	Sponsor: Arcutis Biotherapeutics, Inc.

OBJECTIVES	ENDPOINTS
	
 • vIGA-AD of 'clear' or 'almost clear' at Week 1 
Exploratory efficacy endpoints:
 
 • Exploratory continuous efficacy endpoints include change and percent change in average weekly WI-NRS and daily WI-NRS, EASI, % body surface area (BSA) affected by AD, Children's Dermatology Life Quality Index (CDLQI)/Infant's Dermatitis Quality of Life Index (IDQoL), the Dermatitis Family Impact (DFI), Scoring Atopic Dermatitis (SCORAD), and Patient-oriented Eczema Measure (POEM) at Week 1, Week 2 and Week 4. • Exploratory categorical efficacy endpoints include EASI-75 at Week 1 and Week 2; EASI-50, EASI-90, EASI-100, achievement of at least a 4-point reduction on the WI-NRS, and vIGA-AD of 'clear' at Week 1, Week 2 and Week 4.
Safety	
To assess the safety of ARQ-151 cream 0.05% vs vehicle administered QD x 4 weeks to subjects aged 2-5 years with AD.	
 • Incidence and severity of adverse events (AEs) • Changes and percent change in vital signs • The subject incidence of $\geq 5\%$ weight loss or gain on study • Local tolerability assessments

3 STUDY DESIGN

3.1 Overall Design

This is a Phase 3, parallel group, double blind, vehicle-controlled study in which ARQ-151 cream 0.05% or vehicle is applied QD x 4 weeks to subjects with mild to moderate atopic dermatitis.

At entry, subjects will have $\geq 3\%$ BSA involvement (excluding the scalp, palms, soles) and mild or moderate atopic dermatitis based on vIGA-AD assessment.

 Innovaderm Research ■■■	STATISTICAL ANALYSIS PLAN, Version 1.0
Protocol Number: ARQ-151-315	Sponsor: Arcutis Biotherapeutics, Inc.

Upon determination of eligibility, subjects will be randomized 2:1 to either ARQ-151 cream 0.05% or matching vehicle cream. The randomization will be stratified by vIGA-AD score at baseline ('Mild' vs. 'Moderate'), and by study site.

Caregivers will apply ARQ-151 cream 0.05% or vehicle cream QD to all AD affected areas and any newly appearing AD lesions that arise during the study, except on the scalp. Caregivers should maintain treatment of these areas with study drug for the duration of the study regardless of whether treatable areas of AD clear prior to Week 4/Day 29.

[figure not shown]
Subject participation involves a minimum of 5 clinic visits including Screening, Baseline/Day 1, Week 1/Day 8, Week 2/Day 15, and Week 4/Day 29. The interval between the Screening and Baseline/Day 1 visits could be up to 30 days, therefore the anticipated maximum duration of subject participation is approximately 8 weeks.

At the Week 4/Day 29 visit, subjects may be eligible to enroll in a 12-month, open label extension study (ARQ-151-313) evaluating ARQ-151 cream 0.15% QD and 0.05% QD. All subjects will have the option to enroll into the ARQ-151-313.

The trial design is represented schematically in [Figure 1](#).

	STATISTICAL ANALYSIS PLAN, Version 1.0
Protocol Number: ARQ-151-315	Sponsor: Arcutis Biotherapeutics, Inc.

Figure 1 Study Schema

 Innovaderm Research ■■■	STATISTICAL ANALYSIS PLAN, Version 1.0
Protocol Number: ARQ-151-315	Sponsor: Arcutis Biotherapeutics, Inc.

